- j. Follow-up Treatment Period visits to be performed monthly (every 28 ± 3 days). These visits are only for those subjects who are continuing on study treatment beyond the initial 28-day Early Treatment Period. For those subjects continuing on study beyond 12 months, visits will occur every 2 months ± 3 days. Now that the MTD for daily dosing has been established, if it results in a dose increase for subjects not already receiving the MTD, the study assessments required for the monthly follow-up visits (ie, PK and postdose ECG and vital sign measurements not required) should be performed on Days 1 and 14 of the first month, then monthly for a total of 6 months, then every 2 months thereafter. The same schedule of evaluation will apply to any subjects increased from 50 mg/day to 100 mg/day after 6 months of treatment at 50 mg/day and after the 100 mg dose group is determined not to be a DLT dose cohort. Section 9.6 for study assessments to be performed and the timing of visits.
- k. End-of-Study visit is to be performed 30 days (± 3 days) after last dose of study drug.
- 1. Echocardiograms are to be obtained at Screening, on Day 28, and at Months 3, 6 every 6 months thereafter, and End-of-Study visit and are to include measurement of ejection fraction and assessment for pericardial effusion. Note: If subject has had echocardiogram within 2 months of End-of-Study visit, no need to obtain echocardiogram at End of Study visit. For those subjects who have already had their Month 12 visit, this may be performed at Month 13 and then subsequent echocardiograms may be performed on the same schedule as the MRIs. If pericardial effusion is diagnosed via echocardiogram, subject should be rechecked within 1–3 months to monitor for progression.
- m. Screening MRI should be performed following informed consent and prior to other Screening assessments. Results must be reviewed before the first dose of study drug is administered. MRI to be performed at Month 6 and then every 6 months thereafter. Note: If subject has had MRI within 3 months of End of Study visit, there is no need to obtain MRI at End-of-Study visit.
- n. Subjects on the Phase 1b portion of the study will have study drug held for a one-time drug holiday of at least 14 and up to 28 days with creatinine and cystatin C measurements performed before and immediately after the drug holiday, as well as a predose PK sample prior to restarting study drug.
- o. PK samples will be collected predose at every monthly visit up to and including Month 6 visit for those subjects in the Phase 1b and Phase 2a 50 mg daily portions of the

- study who continue treatment (Follow-Up Treatment Period). NOTE: For subjects re-starting study drug after study drug holiday, collect a predose PK sample prior to restarting study drug.
- Required for Phase 2a 50 mg subjects electing not to participate in PK testing. Based upon the results of testing, a third timepoint may be performed within the first two months of study drug dosing and after consultation with the medical monitor.
- Follow-up Treatment Period visits to be performed monthly (every 28 ± 3 days). For those subjects continuing on study beyond 12 months, visits will occur every 2 months \pm 3 days.

Table 4-3: Schedule of Events for Subjects in Phase 2a Portion of Study Dosed on Monday, Wednesday, and Friday

	Screening		Follow-Up Treatment Period	End of Study ^m					
Assessments	(-28 Days)	Day 1	Day 3	Day 5	Day 8	Day 12 (±1 day)	Day 26 (±1 day)	Every 28 Days (± 3 days) ¹	30 Days from Last Dose (± 3 days)
Informed consent	X								
Medical and PKD history (including genotype, if available)	X								
Physical examination (including weight) ^a	X	X ^l				X	X	X	X
Vital signs ^b	X	X				X	X	X	X
Supine 12-Lead ECG ^c	X	X				X	X	X	X
Clinical laboratory tests ^d	X ⁱ	X^{i}				X	X	X	X
Ocular evaluation ^e	X							X	
Peripheral blood smear	X								X
Iothalamate testing ^f	X					X			
Echocardiogram	X						X ⁿ	X ⁿ	X
Pregnancy test ^g	X	X					X	X Every 3 Months	X
MRI	X							X° Every 6 Months	X
Study drug administration ^h		X	X	X	X	X	X	X	
Concomitant medications	X	X	X	X	X	X	X	X	X
Adverse events		Collect	from the tim	e informed c	consent sign	ed until 30 da	ys after last do	ose of study drug.	

PK sampling ⁱ		X	X	X	X			
Dispense/Collect study drug	X					X	X	X

- a. Complete PE to be done at Screening and End-of-Study visits. Height is only included in the Screening PE. Thereafter, limited PEs will be performed on Days 1, 12, 26, and Day 1 of Months 2 and beyond (See Section 9, Study Assessments, for a description of the body systems, including evaluation for cardiac tamponade and dry mouth by history and exam, and changes in vision to be examined at each visit).
- b. Vital sign measurements consist of sitting blood pressure, pulse rate, respiratory rate, and oral or tympanic temperature. On Day 1, measurements should be performed predose and 1 and 4 hours postdose. See Section 9 for appropriate blood pressure measuring technique. For subjects participating in PK, vital signs are also to be measured 8 hours postdose on Day 1.
- c. Supine 12-Lead ECGs will be performed at Screening, predose, and 1 and 4 hours postdose on Days 1 and 12; predose on Day 26 and Day 1 of Months 2 and beyond; and at End-of-Study visit (repeat 3 times consecutively within 30 minutes [must have an interval of at least 1-2 minutes between ECGs]). If QTc(F) is prolonged to > 60 msec above baseline at any evaluation or to the level of ≥ 480 msec, refer to Section 11.3.3.1 for procedure to be followed. For subjects participating in PK, ECGs are also to be performed 8 hours postdose on Day 1.
- d. Clinical laboratory tests consist of hematology, serum chemistry panel, coagulation, and urinalysis (see Section 9.9 for a complete list of assessments).
- e. Ocular evaluations are to be performed at Screening and at Months 3, 6, 9, 12, 18, and 24. The following assessments should be performed: evaluation of best corrected visual acuity, fundoscopic exam with non-dilated pupils, slit lamp photography of the iris, non-mydriatic photography of retina within the arcade, pils, and optical coherence tomography (OCT) of the optic nerve head and macula.
- f. Optional; to be conducted at selected sites in 3–7 subjects. Second time point should be done on Day 12, 13, 14 or 15, and all study related procedures required on Day 12 may be done at this visit. Based upon the results of testing, a third timepoint may be performed within the first 2 months of study drug dosing and after consultation with the medical monitor.
- g. Urine pregnancy tests are to be done in women of childbearing potential at Screening, predose on Day 1, Day 26, at Month 3 (and every 3 months thereafter up through Month 12), and End-of-Study visits only. For subjects continuing on study past 12 months who have visits every 2 months, testing should be done every 2 months to coincide with their visit schedule. Confirm with serum testing if urine sample is positive.
- h. Subjects will start Phase 2a with an alternative dosing schedule of 150 mg of KD019 on Monday, Wednesday, and Friday of each week.
- i. In the Monday, Wednesday, and Friday dosing schedule of the Phase 2a portion of the study, approximately 5 subjects will have blood samples drawn for PK analyses. If accrual goals have nearly been met, only those who can undergo iothalamate or PK testing will be enrolled. Blood samples will be collected on Study Day 1 (predose, 1, 2, 4, 8, and 24 hours postdose), predose on Study Days 3, 5, and 8, and Study Day 12 (predose, and 1, 2, 4, and 24 hours postdose). (Subjects undergoing iothalamate testing will not undergo PK sampling.) Also, collect PK sample if QTc(F) interval increases by > 60 msec above average baseline or to the level of ≥ 480 msec (see Section 11.3.3.1).
- j. Screening must occur within 28 days of first dose of study drug. Screening evaluations may be combined with Day 1 pre-treatment laboratory evaluations if both are done within 4 days before first dose of study drug. Results must be reviewed before the first dose of study drug is administered.
- k. All protocol-specified clinic visits during the Treatment Period should occur within ± 1 day of the nominal visit day unless otherwise specified.
- 1. Follow-up Treatment Period visits to be performed monthly (± 3 days) for the first 12 months the subject is on study. Thereafter, Follow-up visits are to be performed bimonthly (every 60 ± 3 days). For those subjects continuing on study beyond 12 months, visits will occur every 2 months. See Section 9.6 for study assessments to be performed and the timing of visits.
- m. End-of-Study visit is to be performed 30 days (± 3 days) after last dose of study.
- n. Echocardiograms are to be obtained at Screening, on Day 26, at Months 3, 6 and every 6 months thereafter, and at End-of-Study visit and are to include measurement of ejection fraction and assessment for pericardial effusion. Note: If subject has had echocardiogram within 2 months of End-of-Study visit, no need to obtain echocardiogram at End-of-Study visit. If pericardial effusion is diagnosed via echocardiogram, subject should be rechecked within 1–3 months to monitor for progression.
- o. MRI to be performed at Screening, Month 6 and then every 6 months thereafter. Note: If subject has had MRI within 3 months of End-of-Study visit, there is no need to

obtain MRI at End-of-Study visit.

Table 4-4: Schedule of Events for Subjects in Phase 2a Portion of Study Dosed on Monday and Thursday

	Screening		Early	y Treatmen	t Period ^k		Follow-Up Treatment Period	End of Study ⁿ
Assessments	(-28 Days)	Day 1	Day 8 ¹ (PK Subjects)	Day 11 (±1 day)	Day 18 ¹ (PK Subjects)	Day 25 (±1 day)	Every 28 Days (±3 days) ^m	(30 Days from Last Dose) (±3 days)
Informed consent	X							
Medical and PKD history (including genotype, if available)	X							
Physical examination (including weight) ^a	X	X		X		X	X	X
Vital signs ^b	X	X		X		X	X	X
Supine 12-Lead ECG ^c	X	X		X		X	X	X
Clinical laboratory tests ^d	X ^j	Xi		X		X	X	X
Ocular evaluation ^e	X						X	
Peripheral blood smear	X							X
Iothalamate testing ^f	X					X		
Echocardiogram	X					X ⁿ	X°	X
Pregnancy test ^g	X	X				X	X Every 3 Months	X
MRI	X						X ^p Every 6 Months	X
Study drug administration ^h		X	X	X	X	X	X	
Concomitant medications	X	X	X	X	X	X	X	X
Adverse events		Collect fi	om the time ir	nformed con	sent signed uni	til 30 days afte	r last dose of study dr	rug.
PK sampling ⁱ		X	X	X	X	X		

- a. Complete PE to be done at Screening and End-of-Study visits. Height is only included in the Screening PE. Thereafter, limited PEs will be performed on Days 1, 11, 25, and Day 1 of Months 2 and beyond (See Section 9, Study Assessments, for a description of the body systems, including evaluation for cardiac tamponade and dry mouth by history and exam, and changes in vision to be examined at each visit).
- b. Vital sign measurements consist of sitting blood pressure, pulse rate, respiratory rate, and oral or tympanic temperature. On Day 1 measurements should be performed predose and 1 and 4 hours postdose. For subjects participating in PK, vital signs also are also to be measured 8 hours postdose on Day 1. See Section 9 for appropriate blood pressure measuring technique.
- c. Supine 12-Lead ECGs will be performed at Screening, predose, and 1 and 4 hours postdose on Days 1 and 25; predose on Day 11 and Day 1 of Months 2 and beyond; and at End-of-Study visit (repeat 3 times consecutively within 30 minutes [must have an interval of at least 1-2 minutes between ECGs]). For subjects participating in PK, ECGs also are to be performed 8 hours postdose on Days 1 and 25. If QTc(F) is prolonged to > 60 msec above baseline at any evaluation or to the level of ≥ 480 msec, refer to Section 11.3.3.1 for procedure to be followed.
- d. Clinical laboratory tests consist of hematology, serum chemistry panel, coagulation, and urinalysis (see Section 9.9 for a complete list of assessments). (Need not be repeated if screening visit occurred within 4 days prior to Day 1 visit.)
- e. Ocular evaluations are to be performed at Screening and at Months 3, 6, 9, 12, 18, and 24. The following assessments should be performed: evaluation of best corrected visual acuity, slit lamp photography of the iris, non-mydriatic photography of retina within the arcade, pils, and optical coherence tomography (OCT) of the optic nerve head and macula.
- f. Optional; to be conducted at selected sites in 3–7 subjects. Second time point should be done between Day 22 and 25 and all study related procedures required on Day 25 may be done at this visit. Based upon the results of testing, a third timepoint may be performed within the first 2 months of study drug dosing and after consultation with the medical monitor.
- g. Urine pregnancy tests are to be done in women of childbearing potential at Screening, predose Day 1, Day 25, at Month 3 (and every 3 months through Month 12), and End-of-Study visits only. For subjects continuing on study past 12 months who have visits every 2 months, testing should be done every 2 months to coincide with their visit schedule. Confirm with serum testing if urine sample is positive.
- h. Subjects will start Phase 2a with an alternative dosing schedule of 150 mg on Monday and Thursday of each week.
- i. In the Monday/Thursday dosing schedule of the Phase 2a portion of the study, approximately 5 subjects will have blood samples drawn for PK analyses. If accrual goals have nearly been met, only those who can undergo iothalamate or PK testing will be enrolled. Blood will be collected on Study Day 1 (predose, and 1, 2, 4, 8, and 24 hours postdose); predose on Days 8, 11, and 18; and on Day 25 (predose, and 1, 2, 4, 8, and 24 hours postdose), and predose at every monthly visit thereafter (up to and including the Month 6 visit) (Subjects undergoing iothalamate testing will not undergo PK sampling.) Also, collect PK sample if QTc(F) interval increases by > 60 msec above average baseline or to the level of ≥ 480 msec (see Section 11.3.3.1).
- j. Screening must occur within 28 days of first dose of study drug. Screening evaluations may be combined with Day 1 pre-treatment laboratory evaluations if both are done within 4 days before first dose of study drug. Results must be reviewed before the first dose of study drug is administered.
- k. All protocol-specified clinic visits during the Treatment Period should occur within ± 1 day of the nominal visit day unless otherwise specified.
- 1. This visit is for subjects participating in PK sampling only.
- m. Follow-up Treatment Period visits to be performed monthly (± 3 days) for the first 12 months the subject is on study. Thereafter, Follow-up visits are to be performed bi-monthly (every 60 ± 3 days). For those subjects continuing on study beyond 12 months, visits will occur every 2 months. See Section 9.6 for study assessments to be performed and the timing of visits.
- n. End-of-Study visit is to be performed 30 days (± 3 days) after last dose of study drug.
- o. Echocardiograms are to be obtained at Screening, on Day 25, at Months 3, 6 and every 6 months thereafter, and at End-of-Study visit and are to include measurement of ejection fraction and assessment of pericardial effusion. Note: If subject has had echocardiogram within 2 months of End-of-Study visit, no need to obtain echocardiogram at End-of-Study visit. If pericardial effusion is diagnosed via echocardiogram, subject should be rechecked within 1–3 months to monitor for progression.

p. MRI to be performed at Screening, Month 6, and then every 6 months thereafter. Note: If subject has had MRI within 3 months of End-of-Study visit, there is no need to obtain MRI at End-of-Study visit.

Table 4-5: Timing Window Allowances for PK Sampling, Vital Sign Measurements, and ECGs

Pharmacokinetic Sampling	
Timepoint	Tolerance Window
0 hour	-240 minutes to 0 hour
>0 hour – 2 hour	-2 minutes/+ 2 minutes
4 hour – 8 hour	-5 minutes/+ 5 minutes
24 hour	-30 minutes/+ 30 minutes

Vital Signs		
Timepoint	Tolerance Window	
0 hour	-240 minutes to 0 hour	
>0 hour – 4 hour	-10 minutes/+ 10 minutes	
>4 hour – 8 hour	-30 minutes/+ 30 minutes	

ECG	
Timepoint	Tolerance Window
0 hour	-240 minutes to 0 hour
>0 hour – 4 hour	-10 minutes/+ 10 minutes
>4 hour – 8 hour	-30 minutes/+ 30 minutes

TABLE OF CONTENTS

I	PF	ROCEDURES IN CASE OF EMERGENCY	2
2	SF	PONSOR SIGNATURE	3
3	IN	IVESTIGATOR SIGNATURE	4
4	SY	YNOPSIS	5
5	B	ACKGROUND AND RATIONALE	39
	5.1	Polycystic Kidney Disease	
	5.2	Tesevatinib	

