24 additional subjects were enrolled in the Phase 2a portion of the study using alternative schedules of tesevatinib administration. As the known toxicities of tesevatinib, including diarrhea and rash, may not be tolerable with daily dosing when used long-term in this subject population, alternative dosing schedules of 150 mg of tesevatinib on Monday, Wednesday, and Friday of each week and 150 mg on Monday and Thursday of each week were evaluated during this portion of the study. Several subjects are continuing on this dosing schedule to evaluate long term tolerability. Approximately 5 subjects treated on each alternative dosing schedule had PK samples obtained so that safety, tolerability, and exposure could be evaluated.

In addition, subjects active in the Phase 1b portion had their dose increased or decreased to the established MTD of 100 mg QD. These subjects will continue on daily dosing in order to obtain data on longer term tolerability of daily dosing at the MTD.

In both phases of the study, after the 28-day treatment period, subjects will, at the discretion of the investigator, continue to receive study treatment for 24 months from their first dose or until the development of unacceptable toxicity, noncompliance, or withdrawal of consent by the subject, or investigator decision.

Despite fulfilling the protocol criteria for determining the MTD for daily dosing, the 100 mg daily dose group exhibited a rate of QTc prolongation not acceptable for chronic use. Preliminary data from both the 50 mg daily cohort and the 150 mg Monday and Thursday cohort appear acceptable for chronic use and for further study in terms of safety. The 50 mg daily dose appears to be favorable due to dosing simplicity and to the occurrence of a Grade 3 rash in the 150 mg Monday and Thursday cohort. Additionally, the effect of missed dosing is reduced in the daily dosing cohort. Because of these factors, the 50 mg tesevatinib treatment appears to be the best tolerated dose, and will likely be taken forward in additional studies in ADPKD. In order to generate additional efficacy and safety information for this selected dosing regimen, 15 additional subjects were enrolled as an additional group in the Phase 2a portion of this protocol at a dose of 50 mg daily of tesevatinib. Each of the 15 subjects were required to complete either PK testing as described for other Phase 1b subjects in this protocol or iothalamate testing.

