Study Drug	Tesevatinib is a new chemical entity that inhibits multiple tyrosine kinases (TKs) ErbB family members [EGFR and HER2/ErbB2], vascular endothelial growth factor receptor [VEGFR2/KDR]), and Src family kinases.
Dose and Administration	In the Phase 1b portion of the study, tesevatinib will be administered orally at doses of 50, 100, and 150 mg once daily. Study drug may be taken with or without food, and should be taken at approximately the same time every morning. Subjects should drink a full glass of water (approximately 8 ounces [240 mL]) immediately after study drug administration. In the Phase 2a portion of the study, tesevatinib will be administered on alternative dosing schedules of 150 mg of tesevatinib on Monday, Wednesday, and Friday of each week or 150 mg on Monday and Thursday of each week. Additionally, subjects active in the Phase 1b portion had their dose increased or decreased to the established MTD of 100 mg daily (continuing once-daily administration). If subjects are unable to be seen in clinic on the appropriate protocol specified study day, the schedule may also be Tuesday and Friday or Wednesday and Saturday. However, the same schedule must be adhered to throughout the study. Based on all information generated thus far, the 50 mg tesevatinib treatment is the best tolerated dose, and will likely be taken forward in additional studies in ADPKD. In order to generate additional efficacy and safety information on this selected dosing regimen, 15 additional subjects were enrolled as an additional group in the Phase 2a portion of this protocol at a dose of 50 mg of tesevatinib. Up to 50 additional subjects, with eGFR ≥ 35 mL/min/1.73 m² and ≤ 80 mL/min/1.73 m² and htTKV ≥ 1000 mL will

	of the protocol. Other subjects already enrolled in the study will continue to receive the dose and schedule to which they were assigned or to which they were transferred. Subjects in all cohorts of the study, after the initial 28-day treatment period, will, at the discretion of the investigator, continue to receive study treatment for at least 24 months from their first dose or until the development of unacceptable toxicity, noncompliance, withdrawal of consent by the subject, or investigator decision. Subjects will be provided with an adequate supply of and instructions for taking the study drug. Study drug accounting will be performed at each visit.

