Wednesday, and Friday of each week was explored in the Phase 2a portion of the study to determine if it is more tolerable when used chronically in this subject population. The safety data of the 14 subjects who received 150 mg tesevatinib every Monday, Wednesday and Friday has been reviewed by the Data Safety Committee. There were 3 moderate events: 1 subject had moderate QTc(F) prolongation which resolved with dose modification as well as moderate diarrhea, and 1 subject with moderate rash which improved with topical corticosteroids and emollients. While the tolerability of this schedule appears to be superior to that of dosing tesevatinib 150 mg on a daily schedule, another dosing schedule of tesevatinib 150 mg administered on Monday and Thursday of each week was explored to determine if this dose and schedule would result in fewer moderate toxicities, particularly QTc(F) prolongation. To date, of the 10 subjects receiving 150 mg Monday and Thursday, there was no QTc(F) prolongation; however, 1 subject had a severe (Grade 3) maculopapular skin rash. Thus, while the 150 mg Monday and Thursday administration of tesevatinib generally appears to be a tolerable regimen, the occurrence of the Grade 3 maculopapular skin rash, together with the significant effect of missing any single dose in this regimen, has led to the decision to further evaluate the dose level of 50 mg daily prior to using this dose in a randomized study.

Following the enrollment of the additional 15 subjects in the Phase 2 50 mg dosing cohort, it was concluded that tesevatinib 150 mg in various schedules was associated with skin rash that was not well tolerated. Incidence of moderate QTc prolongation not acceptable for chronic use was associated with tesevatinib 100 mg daily. Tesevatinib 50 mg daily appeared to be a well-tolerated dose in patients with ADPKD, although some acneiform rash occurred. The study will enroll approximately 50 more subjects at the dose of 50 mg daily in order to increase the robustness of the safety data in subjects with ADPKD treated with tesevatinib.

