11.2 Dose Escalation and Entry of Subjects into the Next Cohort

In the Phase 1b portion of the study, cohorts will be filled sequentially. Once assigned to a cohort, each subject will continue to be treated at the same dose level and schedule throughout the course of the study. For subjects dosed with 50 mg/day: If the 100-mg cohort has been evaluated and the determination made that 100 mg/day is not the MTD, and study enrollment is opened at the 150 mg dose, then subjects initially treated in the 50 mg dose cohort will have the option of increasing their dose of tesevatinib to 100 mg/day after they have received a minimum of 6 months of treatment at the 50 mg/day dose. The participating study centers will be notified (eg, phone, e-mail, telefax) and confirmed in writing when accrual to a cohort has been closed.

Accrual to the next cohort will not occur until the 28-day data from a previous cohort have been received and all safety data have been reviewed.

At the end of each dosing cohort, a Data Safety Committee including an independent safety monitor with significant clinical expertise in polycystic kidney disease will review all safety data (PK, safety labs, ECGs, echocardiogram, and AEs). An independent cardiologist will review all ECGs and echocardiograms. Once all data has been reviewed it will be determined whether dose escalation may occur. Dose escalation to the next higher dose will not begin until the safety data from the preceding dose cohort has been evaluated and deemed acceptable. Specifically, the decision to progress to the next higher dose will be made after the safety data through a minimum of 28 days of follow-up are reviewed for at least 8 subjects in the preceding dose cohort and it is determined that it is safe to proceed to the next dose level.

Dose escalation to the next planned tesevatinib dose will be reviewed and dose adjustments may be made if any of the following safety criteria are met:

• ≥ 25% of subjects in a cohort experience a severe (or higher) **related** adverse event in the same organ or body system

Any other related adverse event occurs in a subject that is deemed by the investigator to
pose an unacceptable risk to other participants in the study such as symptoms of cardiac
tamponade

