After the MTD for daily dosing was established, 24 additional subjects were enrolled in the Phase 2a portion of the study and treated at 150 mg/day using alternate schedules of tesevatinib administration. As the known toxicities of tesevatinib, including diarrhea and rash, may not be tolerable with daily dosing when used long-term in this subject population, alternative dosing schedules of either Monday, Wednesday, and Friday of each week or Monday and Thursday of each week were evaluated during this portion of the study. Additionally, as the MTD for daily dosing has been determined to be 100 mg/day, subjects active in the Phase 1b portion had their dose either increased or decreased to this dose. These subjects have continued on daily dosing in order to evaluate long-term tolerability of the daily dosing regimen.

Drug holiday may start 14 days after dose escalation to the MTD or any time after 6 months of tesevatinib administration.

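### The protocol keeps transferred Phase 1b subjects on 100 mg daily to study long-term tolerability while stating that QTc prolongation at that dose is not acceptable for chronic use, and it does not reconcile the two

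*Protocol*

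**What the plan says.** **Continuation at 100 mg.** The protocol Synopsis, Study Design, states that "subjects active in the Phase 1b portion had their dose increased or decreased to the established MTD of 100 mg QD" and continues: "These subjects will continue on daily dosing in order to obtain data on longer term tolerability of daily dosing at the MTD". Section 11.2 says nearly the same: "These subjects have continued on daily dosing in order to evaluate long-term tolerability of the daily dosing regimen". Sections 7.2 and 7.2.2 also report the move, there for long-term safety data. The Synopsis, Dose and Administration, after describing the planned group of up to 50 further subjects, says "Other subjects already enrolled in the study will continue to receive the dose and schedule to which they were assigned", and the sentence goes on to cover any dose to which they were transferred. Treatment may run to 24 months from first dose (Dose and Administration says at least 24 months).

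**Judgement on 100 mg.** Study Design also says that "the 100 mg daily dose group exhibited a rate of QTc prolongation not acceptable for chronic use". Sections 5.4.2 and 7.2.2 repeat this, and Section 5.2.2.2.3 puts it as: "Incidence of moderate QTc prolongation not acceptable for chronic use was associated with tesevatinib 100 mg daily". Sections 5.2.2.2.3 and 14.1 trace the turn to 50 mg to moderate QTc prolongation in 2 subjects.

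**Raising subjects to 100 mg.** Section 11.2 says 50 mg subjects "will have the option of increasing their dose of tesevatinib to 100 mg/day" after at least 6 months, on the condition that 100 mg is found not to be the MTD. Table 4-2 footnote j takes the MTD as established and sets visits "if it results in a dose increase for subjects not already receiving the MTD", with no postdose ECG required. Section 9.6 sets a matching schedule for Phase 1b subjects going from 50 mg to 100 mg.

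**The concern.** Two statements in one version of the protocol point in opposite directions for the same people on the same regimen. The dosing text continues them at 100 mg daily so that longer exposure can be observed. The safety text says the QTc findings at 100 mg daily rule out long exposure.

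The risk concerned is cardiac. Section 11.3.3 itself notes that acquired long QT can lead to life-threatening arrhythmia and that individual risk with this drug is hard to predict. Sites working from different sections could treat the same subject differently, and an ethics board reading the Synopsis could not tell which statement governs.

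**Working it through.** There is no planned figure to reproduce. The check is a comparison of texts, with a little arithmetic for scale.

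**1. Same regimen?** Yes. Both statements concern 100 mg once daily in this study.

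**2. Both current?** Yes, on the wording.
- The continuation sentence in Study Design is in the future tense.
- The Dose and Administration sentence follows text on a group that was still to be enrolled, so it is not only a record of an older stage.
- The chronic-use statement stands in the same version and the same Synopsis section.

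**3. Is the continued treatment chronic?** Yes. It may last 24 months from first dose, and its stated aim is longer-term tolerability.

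**4. Does anything reconcile them?** Nothing found.
- No available section moves subjects off 100 mg daily or gives a reason for continuing despite the QTc judgement.
- Sections 9.10 and 11.3.3.1 give a rule for the individual subject. If QTc(F) rises more than 60 msec or reaches 480 msec, drug is withheld, a PK sample is taken, the central reading is awaited, and dose reduction or removal is discussed. The rule acts after a threshold is crossed. It does not say whether the group should stay on the dose.
- SAP Section 2.2.1 describes the 50-to-100 mg option in the past tense and does not address subjects continuing on 100 mg.

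**5. Escalation text.**

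| Place | What it does | Status |
|---|---|---|
| Section 11.2 | Offers the increase if 100 mg is not the MTD | Condition lapsed: Sections 5.2.2.2.3, 7.2 and 7.2.2 give 100 mg as the daily MTD |
| Synopsis (Study Design), Sections 7.2 and 7.2.2 | Report the option | Past tense |
| Table 4-2 footnote j | Sets visits after an increase; no postdose ECG required | Worded as current |
| Section 9.6 | Days 1 and 14, monthly to 6 months, then every 2 months; predose ECG | Worded as current |

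Footnote j and Section 9.6 schedule visits; they do not themselves authorise an increase. The missing postdose ECG still matters if anyone is raised. Section 5.3.1 reports that at 50 mg the peak QTcF increase was 11–15 ms at 4 hours postdose on Day 14, against a time average of 4–6 ms. It also reports, from earlier studies, that prolongation grew with plasma concentration.

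**6. How many subjects?** Phase 1b enrolled 9 + 8 + 5 = 22 (Sections 5.2.2.2.3 and 5.4.2). Three of the 5 at 150 mg daily withdrew consent, so at most 22 − 3 = 19 could still be on drug. The actual number is not stated.

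**7. How strong is the QTc signal?** There are 2 subjects and no stated denominator. Exact (Clopper-Pearson) 95% intervals under assumed denominators:

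| Assumed number exposed to 100 mg | Rate | 95% interval |
|---|---|---|
| 8 (original cohort only) | 2/8 = 25% | 3.2% to 65.1% |
| 13 (8 + 5) | 2/13 = 15.4% | 1.9% to 45.4% |
| 17 (8 + 9) | 2/17 = 11.8% | 1.5% to 36.4% |
| 22 (all Phase 1b, outer limit) | 2/22 = 9.1% | 1.1% to 29.2% |

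The contradiction does not depend on which row applies. It rests on the protocol's own judgement, not on an estimated rate.

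**The case against.** The best defence is that much of this text is left over from a completed stage. Phase 1b is described as finished, and continuation is at the investigator's discretion. Given the 24-month limit and the later enrolment of groups of 24 and then 15, few or no subjects may remain on 100 mg. The QTc(F) rule protects individuals. After a 50-to-100 mg increase, Section 9.6 asks for assessments on Days 1 and 14 and then monthly for 6 months. Finally, some text between the visible part of Section 5.2.2.2.3 and Section 5.2.2.3 was not available for this check. Section 5.3.1 refers back to Section 5.2.2.2.3 for QTc events, so further handling could be described there.

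Much of this stands, and it rules out several stronger readings that a reader might infer:

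- **That sites may now raise a 50 mg subject to 100 mg under Section 11.2.** The condition has lapsed, and other sections treat the option as past. Active Phase 1b subjects are also said to have been moved already, and the text does not concern the Phase 2a 50 mg or SILK groups.
- **That 22 subjects are affected, or that the QTc rate is 25%.** The first ignores the reported withdrawals; the second assumes a denominator.
- **That data at 100 mg have lost all purpose.** The protocol does not say so. It links long-term tolerability to diarrhea and rash as well, which a QTc finding does not settle.

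The defence does not reach the main point. The continuation sentences in the Synopsis are written as current instructions, and nothing available squares them with the chronic-use statement.

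**Conclusion.** The contradiction is real and should be resolved, because following the dosing text as written means chronic treatment at a dose that the same document calls unacceptable for chronic use. The retained visit schedules in Table 4-2 footnote j and Section 9.6 add to the confusion but are secondary.

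In practice the exposure lies anywhere from no subjects to 19, and the underlying signal is 2 cases of moderate QTc prolongation. The conclusion assumes that the unavailable text contains no reconciling statement. It takes no position on which dose is right.

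**What to change.** Reconcile the Synopsis (Study Design; Dose and Administration) and Section 11.2 with the chronic-use statement in one of two ways:

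- give one current instruction for Phase 1b subjects on 100 mg daily; or
- place a justification for continuing directly beside the chronic-use statement.

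State how many subjects, if any, are still on 100 mg daily. If there are none, saying so and putting the continuation sentences in the past tense is enough.

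If increases to 100 mg are closed, mark the text in Table 4-2 footnote j, Section 9.6 and Section 11.2 as historical. Do the same for the drug-holiday timing tied to escalation to the MTD in Sections 7.2.2, 9.3.4, 11.1 and 11.2. The choice of dose is for the sponsor and the Data Safety Committee.

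The cost is an amendment to existing sentences and a letter to sites. The rewording itself adds no subjects or procedures. If continuation ends, some longer-term data at 100 mg are forgone.
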